3.5.2. Reactogenicity Data

The reactogenicity data collected in the study e-diary will include: local reactions (erythema/redness, induration/swelling, and pain at the injection site) and systemic events (fever, vomiting, headache, fatigue, new or worsening muscle pain, and new or worsening joint pain). The e-diary will record reactogenicity data from Day 1 to Day 7 starting on the day of each vaccination.

Participants reporting local reactions and systemic events on any day within the 7-day period after each vaccination and also for any vaccination will be descriptively summarized by vaccine regimen. Severities of local reactions and systemic events reported after each vaccination and also for any vaccination will also be descriptively summarized by vaccine regimen. Exact 2-sided 95% CIs of the percentages will also be presented.

All reactogenicity endpoints will be summarized as number and percentage of participants with events by vaccine regimen. Additionally, exact 2-sided 95% CIs of the percentages will be calculated using the Clopper-Pearson method.

3.5.2.1. Local Reaction Endpoints

Local Reactions: Presence or Absence

The presence of redness or swelling is to be recorded in the e-diary as "yes" or "no." If redness or swelling is present, then a second question is to appear requesting the size of the affected area; otherwise, no question is to appear. A measuring device with a scale ranging from 1 to 21 is to be used to measure the largest diameter in whole-number increments. Measurements are to be rounded up to the nearest whole number. If the area is larger than the measuring device can measure, "21+" is to be selected. Measuring device units are converted to centimeters according to the scale: 1 measuring device unit = 0.5 centimeters (cm).

The presence of redness and swelling is defined according to the following scale:

- = ., if missing
- = "No," if no or minimal redness or swelling is present, <2.5 cm (<5 measuring device units)
- = "Yes," if \geq 2.5 cm (\geq 5 measuring device units)

These categories (., "no," "yes") as assessed on Day 1 to Day 7 after each vaccination will be used for derivation of the variables below.

CCI

• Presence of each local reaction on any day (Day 1 to Day 7) after each vaccination and after any vaccination.

CCI

• Presence of any local reaction on any day (Day 1 to Day 7) after each vaccination and after any vaccination.

For each local reaction, the derivation of "any day" is given in Table 6.

Table 6. **Derived Variables for Each Local Reaction**

	Variable	Yes (1)	No (0)	Missing (.)
CCI				
	Any day	Participant reported the	Participant reported the	Participant did not report on
	(Day 1 to	reaction as "yes" on any day	reaction as "no" on all 7 days	the reaction on any of the
	Day 7)	(Day 1 to Day 7)	or as a combination of "no"	7 days
			and missing on all 7 days	

"any day" is given in Table 7. For any local reaction, the derivation of CCI

Table 7. **Derived Variables for Any Local Reaction**

	Variable	Yes (1)	No (0)	Missing (.)
CCI				
	l			
	Any day	Participant reported any	Participant reported all	Participant did not report on
	(Day 1 to	reaction as "yes" on any day	reactions as "no" on all 7	any of the reactions on any of
	Day 7)	(Day 1 to Day 7)	days or as a combination of	the 7 days
			"no" and missing on all 7	
			days	

Maximum Severity for Local Reactions

Erythema/redness and induration/swelling are measured and recorded in measuring device units (range: 1-21+) and then categorized as absent, mild, moderate, or severe based on the grading scale in Table 8. Pain at the injection site will be assessed by the participants as mild, moderate, or severe according to the grading scale in Table 8.

Table 8. **Local Reactions Grading Scale**

	Mild (Grade 1)	Moderate (Grade 2)	Severe (Grade 3)	Potentially Life Threatening
				(Grade 4)
Pain	No interference with	Some interference	Significant; prevents	Emergency room visit
	activity	with activity	daily activity	or hospitalization for
				severe pain
Erythema/	2.5 cm to 5.0 cm	>5.0 cm to 10.0 cm	>10 cm	Necrosis or
Redness	(5 to 10 measuring	(11 to 20 measuring	(≥21 measuring	exfoliative dermatitis
	device units)	device units)	device units)	
Induration/	2.5 cm to 5.0 cm	>5.0 cm to 10.0 cm	>10 cm	Necrosis
Swelling	(5 to 10 measuring	(11 to 20 measuring	(≥21 measuring	
	device units)	device units)	device units)	

Only an investigator or medically qualified person is able to classify a participant's local reaction as Grade 4. A Grade 4 reaction will be recorded in the CRF and is not collected in the e-diary. Grade 4 could also be determined if a reaction is reported as an SAE.

The maximum severity (highest grading) of each local reaction within 7 days after each vaccination will be derived. The maximum severity will be derived as follows:

- = ., if values are missing for all days (Day 1 to Day 7)
- = 0, if the participant reports all reactions as "no" or a combination of missing and "no" for all days (Day 1 to Day 7)
- = highest grade (maximum severity) within 7 days after vaccination, if the answer is "yes" for at least 1 day

Duration of Each Local Reaction

For participants experiencing any local reactions (or those with a derived reaction as described in Table 6 and Table 8), the maximum duration (last day of reaction – first day of reaction + 1) will be derived for each study vaccination. Resolution of the event is the last day on which the event is recorded in the e-diary or the date the event ends if it is unresolved during the participant diary-recording period (end date collected on the CRF), unless chronicity is established. If there is no known end date, the duration will be considered unknown and set to "missing." However, if an event is ongoing at the time of a subsequent vaccination, the end date/day for the ongoing event will be the date/day that the next vaccination is administered, which will be used for the duration computation. Participants with no reported reaction have no duration.

Onset of Each Local Reaction

The onset day of each local reaction and any local reaction will be derived.

The onset day for each local reaction is the first day the participant reports the local reaction, even if the reaction later becomes more severe. The onset day for any local reaction will be the first day of any of the 3 local reactions, regardless of severity. Onset day will be "missing" for participants without the indicated local reaction.

In summary, the following variables will be derived for local reactions:

- 1. Each local reaction on and after any vaccination and after any vaccination.
- 2. Any local reaction on any day (Day 1 to Day 7) after each vaccination and after any vaccination.
- 3. Maximum severity of each local reaction on any day (Day 1 to Day 7) after each vaccination and after any vaccination.
- 4. Maximum duration of each local reaction after each vaccination.
- 5. Onset day of each local reaction after each vaccination.
- 6. Onset day of any local reaction after each vaccination.

3.5.2.2. Systemic Event Endpoints

Systemic events will be reported via the e-diary. Participants will be asked to assess the severity of each event as mild, moderate, or severe as specified in Table 9. Only an investigator or medically qualified person is able to classify a participant's systemic event as Grade 4, after physical examination or documentation from another medically qualified source.

Table 9. Systemic Event Grading Scale

	Mild (Grade 1)	Moderate (Grade 2)	Severe (Grade 3)	Potentially Life Threatening (Grade 4)
Vomiting	1-2 times in 24 hours	>2 times in 24 hours	Requires IV hydration	Emergency room visit or hospitalization for hypotensive shock
Headache	No interference with activity	Some interference with activity	Significant; prevents daily activity	Emergency room visit or hospitalization for severe headache
Fatigue/ Tiredness	No interference with activity	Some interference with activity	Significant; prevents daily activity	Emergency room visit or hospitalization for severe fatigue
New or worsening muscle pain	No interference with activity	Some interference with activity	Significant; prevents daily activity	Emergency room visit or hospitalization for severe new or worsening muscle pain
New or worsening joint pain	No interference with activity	Some interference with activity	Significant; prevents daily activity	Emergency room visit or hospitalization for severe new or worsening joint pain

Abbreviation: IV = intravenous.

For each systemic event, the following variables will be derived, similar to local reactions:

- 1. Each systemic event on any day (Day 1 to Day 7) after each vaccination and after any vaccination.
- 2. Any systemic event (including fever as described in Section 3.5.2.3) on day (Day 1 to Day 7) after each vaccination and after any vaccination.
- 3. Maximum severity of each systemic event on any day (Day 1 to Day 7) after each vaccination and after any vaccination.
- 4. Maximum duration of each systemic event after each vaccination.
- 5. Onset day of each systemic event after each vaccination.
- 6. Onset day of any systemic event after each vaccination.

The derivation of these variables is similar to the derivation of the variables for local reactions (Section 3.5.2.1).

3.5.2.3. Temperature

Oral temperature will be collected in the e-diary, in the evening, daily for 7 days after vaccination. It will also be collected at any time during the e-diary data collection periods that fever is suspected. The highest temperature for each day will be recorded in the e-diary. The protocol defines fever as an oral temperature $\geq 38.0^{\circ}$ C ($\geq 100.4^{\circ}$ F). Fever will be categorized as specified in Table 10.

Table 10. Scale for Fever

Mild (Grade 1)	38.0-38.4°C (100.4-101.1°F)	
Moderate (Grade 2)	38.5-38.9°C (101.2-102.0°F)	
Severe (Grade 3)	39.0-40.0°C (102.1-104.0°F)	
Potentially life threatening (Grade 4)	>40.0°C (>104.0°F)	

Similar to the derivations of systemic events and local reactions, fever will be derived for the following:

- 1. Fever on any day (Day 1 to Day 7) after each vaccination and after any vaccination.
- 2. Highest fever (maximum severity) on any day (Day 1 to Day 7) after each vaccination and after any vaccination.
- 3. Maximum duration of fever after each vaccination.
- 4. Onset day of fever after each vaccination.

Temperatures <35.0°C and >42.0°C will be excluded from the analysis.

3.5.3. E-Diary Completion

For any given day, an e-diary will be transmitted and considered complete if all expected data (the 3 local reactions and the 6 systemic events, including fever) are available. If all data are missing for all items on the e-diary, for all days following vaccination, the e-diary will be considered not transmitted. An e-diary will be considered completed if all expected data for all days are available (ie, not missing) and data are valid. Otherwise, the e-diary will be considered incomplete.

For e-diaries, an indicator variable for the percentage of days without data will be derived as follows:

- = 1, if data have been transmitted, and are complete for 7 days (100%)
- = 2, if data have been transmitted, and are complete for 6 days (\geq 75% to <100%)
- = 3, if data have been transmitted, and are complete for 4 or 5 days (\geq 50% to <75%)

- = 4, if data have been transmitted, and are complete for 2 or 3 days ($\geq 25\%$ to $\leq 50\%$)
- = 5, if data have been transmitted, and are complete for 0 to 1 day (<25%)

4. ANALYSIS SETS (POPULATIONS FOR ANALYSIS)

Data for all participants will be assessed to determine if participants meet the criteria for inclusion in each analysis population prior to unblinding and releasing the database. Classifications will be documented per standard operating procedures.

4.1. Evaluable Immunogenicity Populations

The evaluable immunogenicity population assessed at Month 7 (EI7) will be the primary population for the immunogenicity analyses. The EI7 population will consist of all study participants who:

- Have been enrolled (signed the ICD) and received all 3 doses of the investigational product to which they were randomized,
- Have had blood drawn for assay testing within 28 to 47 days after Visit 4,
- Have valid and determinate assay results for either toxin A or toxin B for the specified analysis at Month 7, and
- Have no major protocol deviations.

The evaluable immunogenicity population assessed at Month 12 (EI12) will be the population for the immunogenicity analyses at Month 12. The EI12 population will consist of all study participants who:

- Have been enrolled (signed the ICD) and received all 3 doses of the investigational product to which they were randomized,
- Have had blood drawn for assay testing within 165 to 200 days after Visit 4,
- Have valid and determinate assay results for either toxin A or toxin B for the specified analysis at Month 12, and
- Have no major protocol deviations.

4.2. Modified Intent-to-Treat Population

The modified intent-to-treat (mITT) population will include all randomized participants who have received at least 1 vaccination and have at least 1 valid and determinate assay result for either toxin A or toxin B for the proposed analysis time points. Participants will be summarized according to the vaccine group to which they were randomized.

Immunogenicity analyses using the mITT population will be conducted only if the mITT population size exceeds the size of the EI7 (or EI12 as appropriate) population by >5%. If the difference between the sizes of the mITT and EI7 (or EI12 as appropriate) populations is \leq 5%, only the analyses based on the EI7 (or EI12 as appropriate) population will be provided.

4.3. Safety Analysis Population

The safety analysis population (SAF) will include all participants who have received at least 1 dose of the investigational product. For reactogenicity analyses by dose, participants who received a different investigational product regimen from the regimen they were assigned will be included in the safety population for the summaries of individual vaccinations up until the point their regimen differs from the assigned regimen, at which point they would no longer be included. For AE analysis, such participants will be included in the AE summary in the group according to the second vaccine dose received.

4.4. Other Analysis Sets

No other analysis set will be defined for the study.

5. GENERAL METHODOLOGY AND CONVENTIONS

The immunogenicity data will be summarized according to the vaccine regimen as received for participants in the EI7 (or EI12 as appropriate) population and according to the vaccine regimen as randomized in the mITT population.

For the assessments of seroresponse difference at Month 7, Month 12, and at Month 7 and Month 12 by age group, as well as the summary of fold rise, the *C difficile* toxin A– or toxin B–specific neutralizing antibody concentration levels below the LLOQ or denoted as BLQ will be set to the appropriate LLOQ value.

For GMC and GMFR analysis, the antibody levels that are below LLOQ or denoted as BLQ will be assigned a value of $0.5 \times \text{LLOQ}$. Missing serology data will not be imputed.

5.1. Hypotheses and Decision Rules

5.1.1. Analysis of the Primary Immunogenicity Endpoint

The primary objective of assessing noninferiority of the 2-dose regimen to the 3-dose regimen will be tested for each of *C difficile* toxin A– or toxin B–specific neutralizing antibody levels determined at 1 month after the last vaccination using participants in the EI7 population.

The 2 null hypotheses (H_0) for noninferiority are:

$$H_{01}: \ln(\mu_2) - \ln(\mu_3) \le -\ln(1.5)$$

where $ln(\mu_2)$ and $ln(\mu_3)$ are the means of the natural logarithm-transformed C difficile toxin A— or toxin B—specific neutralizing antibody levels from participants receiving the C difficile vaccine 2-dose regimen and 3-dose regimen, respectively, measured 1 month after the last vaccination (Month 7) of the vaccine regimen. Baseline adjusted GMC ratios, along with 95% CIs, will be computed for each of toxin A— or toxin B—specific neutralizing antibody levels and will be used to test the null hypothesis.

and

 H_{02} : $P_2 - P_3 \le -10\%$

where P₂ and P₃ are the percentage of participants with a seroresponse in *C difficile* toxin A– or toxin B–specific neutralizing antibody levels from participants receiving the *C difficile* vaccine 2-dose regimen and 3-dose regimen, respectively, measured 1 month after the last vaccination (Month 7) of the vaccine regimen. A participant achieves seroresponse if the participant has at least a 4-fold rise in the respective antibody levels for the proposed analysis time point relative to the levels from baseline. Baseline concentration is defined as the antibody concentration results from the blood drawn before vaccine Dose 1. The difference in percentage of participants achieving seroresponse and the associated 95% CIs will be calculated using the Miettinen and Nurminen method.

The primary immunogenicity objective of the noninferiority of the 2-dose regimen to the 3-dose regimen will be achieved if the lower limit of the 2-sided 95% CI for the GMC ratio (2-dose/3-dose) is > 0.67 and the lower limit of the 2-sided 95% CI for the difference between the regimens (2-dose) in the percentage of participants achieving seroresponse is > -10% for both toxin A— and toxin B—specific neutralizing antibody levels assessed 1 month after the last vaccination.

A secondary analysis will be performed based on the mITT population as appropriate. For this analysis participants will be summarized according to the vaccine group to which they were randomized. Missing serology data will not be imputed.

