For each of toxin A– and toxin B–specific neutralizing antibody levels, the GMC ratio of the 2-dose regimen to the 3-dose regimen at Month 7 and Month 12 will be evaluated by an analysis of covariance (adjusted for baseline antibody concentrations) and the corresponding 95% CIs. Two (2)-sided 95% CIs will be constructed by obtaining a CI for the mean of the logarithmically transformed assay results based on the Student t distribution, and transforming the confidence limits back to the original units. For each of the toxin A– and toxin B–specific neutralizing antibody levels, the difference between the 2-dose and 3-dose regimens in the percentage of participants achieving seroresponse at Month 7 and Month 12 will be computed, along with 95% CIs, using the Miettinen and Nurminen method. Seroresponse will be considered achieved if a participant has at least a 4-fold rise from baseline in the respective antibody concentration following vaccination. Baseline concentration is defined as the antibody concentration results from the blood drawn before vaccine Dose 1. Antibody concentration values below the LLOQ or denoted as below the limit of quantitation (BLQ) will be set to 0.5 × LLOQ for analysis.

All safety and reactogenicity endpoints will be summarized as proportions of participants with events by vaccine group. Additionally, exact 2-sided 95% CIs for proportions will be calculated using the Clopper-Pearson method.

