
Table 6. Power Analysis (Primary Immunogenicity Objective: Noninferiority for GMC ratio)

Criteria	Neutralizing Antibody	Standard Deviation (Log Value) ^a	Assume Observed Log GMC Difference	Number of Evaluable Participants per Regimen	Power ^b	Power to Meet NI for Both Toxins at 1 Month After Dose 3
Lower limit of	Toxin A	0.794	0.2	784	99.92%	96.91%
95% CI for GMC ratio (2 doses/3 doses) > 0.67	Toxin B	1.059	0.2	784	96.99%	

Abbreviations: GMC = geometric mean concentration; NI = noninferiority.

Table 7. Power Analysis (Primary Immunogenicity Objective: Noninferiority for Difference in Seroresponse)

Criteria	Neutralizing Antibody	Observed % of seroresponse from 3-dose group ^a	Assume % of seroresponse from 2-dose group	Number of Evaluable Participants per Regimen	Power ^b	Power to Meet NI for Both Toxins at 1 Month After Dose 3
Lower limit of 95% CI for difference in seroresponse rate (2 doses minus 3 doses) > -10%	Toxin A	91.8%	86%	784	96.14%	93.43%
	Toxin B	93.7%	86%	784	97.18%	

Note: Seroresponse = Participant achieves at least a 4-fold rise after the last vaccination

If the primary immunogenicity objective is met, the secondary immunogenicity objective will be evaluated by the same criteria. For the secondary immunogenicity objective, if the noninferiority criterion for the GMC ratio is met at Month 12, then the evaluation of the difference between regimens in seroresponse at Month 12 will follow.

A sufficient number of participants will be screened to achieve 1960 participants randomly assigned to investigational product and 1568 evaluable participants (assuming a maximum study nonevaluable rate of 20% and a randomization ratio of 1:1), for an estimated total of 784 evaluable participants per vaccine group in order to meet the primary immunogenicity objectives.

a. Reference Study B5091009 tested by new assay, 1 month after Dose 3.

b. At 0.05 alpha level (2-sided).

a. Reference Study B5091009.

b. At 0.05 alpha level (2-sided).

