1. VERSION HISTORY

The statistical analysis plan (SAP) Version 1 for Study B5091019 is based on the protocol dated 02 May 2019. This SAP amendment (Version 2) is updated to align with some changes to the analysis as mentioned in Table 1.

Table 1. Summary of Major Changes in SAP Amendments

SAP Version	Change	Rationale			
1	Not applicable	Not applicable			
2	Minor updates in Section 2.2.2, Section 3.4.3, Section 3.5.2.1, Section 4.1, Section 4.2, Section 4.3, Section 5, Section 6 and Section 7.2.	 Following regulatory consultation, antibody concentration levels below the lower limit of quantitation (LLOQ) are imputed to the appropriate LLOQ value when determining seroresponse. Clarification was added to the duration calculations for reactogenicity events, based on Food and Drug Administration (FDA) comments for the study data standardization plan. Clarifications were added regarding the evaluable immunogenicity populations determined at Month 7 and Month 12. Immunogenicity analysis using the modified intent-to-treat (mITT) population will be limited based on the relative size of the mITT population. Clarification was added to identify participants to be included in specific vaccine regimens within the safety analysis population. Clarification was added to identify individual participant data cutoff time points for inclusion in the interim analyses. 			

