Criteria	Neutralizing Antibody	Standard Deviation (Log Value) ^a	Assumed Observed Log GMC Difference	Number of Evaluable Participants per Regimen	Power ^b	Power to Meet NI for Both Toxins at 1 Month After Dose 3
Lower limit of 95% CI for GMC ratio	Toxin A	0.794	0.2	784	99.92%	96.91%
(2 doses/3 doses) >0.67	Toxin B	1.059	0.2	784	96.99%	

Abbreviations: GMC = geometric mean concentration; NI = noninferiority

- a. Reference Study B5091009 tested by the new assay, 1 month after Dose 3.
- b. At 0.05 alpha level (2-sided).

Table 4. Power Analysis (Primary Immunogenicity Objective: Noninferiority for Difference in Seroresponse)

Criteria	Neutralizing Antibody	_	Assumed % of Seroresponse From 2-Dose Group	-	Power ^b	Power to Meet NI for Both Toxins at 1 Month After Dose 3
Lower limit of 95% CI for difference of	Toxin A	82.3%	79.3%	784	93.93%	93.64%
seroresponse rate (2 doses minus 3 doses) > -10%	Toxin B	92.4%	89.4%	784	99.7%	

Abbreviations: BLQ = below the limit of quantitation; LLOQ = lower limit of quantitation; NI = noninferiority.

Note: Seroresponse = participant achieves at least a 4-fold rise after the last vaccination (antibody concentration levels below the LLOQ or denoted as BLQ will be set to the appropriate LLOQ value).

- a. Reference Study B5091009.
- b. At 0.05 alpha level (2-sided).

A sufficient number of participants will be screened to achieve 1960 participants randomly assigned to investigational product and 1568 evaluable participants (assuming a maximum study nonevaluable rate of 20%), for an estimated total of 784 evaluable participants per vaccine group in order to meet the primary immunogenicity objectives.

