3.4.3. Baseline Serostatus

Individual participants' baseline serostatus (prior to the first vaccination) will be defined based on the LLOQ values for *C difficile* toxin A– and toxin B– specific neutralizing antibody levels as outlined below.

- Toxin A+: baseline toxin A–specific neutralizing antibody level ≥ LLOQ for toxin A-specific neutralizing antibody level
- Toxin A—: baseline toxin A—specific neutralizing antibody level < LLOQ for toxin A-specific neutralizing antibody level
- Toxin B+: baseline toxin B–specific neutralizing antibody level ≥ LLOQ for toxin B-specific neutralizing antibody level
- Toxin B—: baseline toxin B—specific neutralizing antibody level <LLOQ for toxin B-specific neutralizing antibody level

In addition, the following 4 groups will also be defined.

- Toxin A+/toxin B+: baseline serostatus is both toxin A+ and toxin B+
- Toxin A+/toxin B-: baseline serostatus is toxin A+ and toxin B-
- Toxin A-/toxin B+: baseline serostatus is toxin A- and toxin B+
- Toxin A-/toxin B-: baseline serostatus is both toxin A- and toxin B-

CCI

For the assessments of

seroresponse difference at Month 7, at Month 12, and at Month 7 and Month 12 by age group, as well as the summary of fold rise, the *C difficile* toxin A– or toxin B–specific neutralizing antibody concentration levels below the LLOQ or denoted as below the limit of quantitation (BLQ) will be set to the appropriate LLOQ value.

For GMC and GMFR analysis, the antibody levels that are below the LLOQ or denoted as BLQ will be assigned a value of $0.5 \times LLOQ$.

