5.2.2. Analyses for Continuous Endpoints

The *C difficile* toxin A– or toxin B–specific neutralizing antibody levels at each blood sampling time point will be summarized by GMCs and the associated 95% CIs for each vaccine regimen. The GMC will be calculated as the mean of the assay levels after making the logarithm transformation and then exponentiating the result. The 2-sided 95% CI will be constructed by obtaining the CI for the mean of the logarithmically transformed assay results based on the t-distribution and then exponentiating the limits.

The adjusted GMCs and the corresponding GMC ratios will be calculated using analysis of covariance on logarithmically transformed neutralizing antibody levels at the time point with baseline antibody levels as a covariate and dose regimen as a fixed factor. The SAS GLM procedure will be used to estimate the GMC ratios and the associated 95% CIs.

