6. ANALYSES AND SUMMARIES

6.1. Primary Endpoints

6.1.1. Primary Endpoints for Immunogenicity

The primary objective for immunogenicity is to establish noninferiority of the 2-dose regimen to the 3-dose regimen for each of *C difficile* toxin A– and toxin B–specific neutralizing antibody levels by adjusted GMC ratios, adjusted for baseline antibody level, and by the difference between the regimens in the percentage of participants achieving seroresponse, evaluated at 1 month after the last vaccination (Month 7).

6.1.1.1. *C difficile* Toxin A– and Toxin B–Specific Neutralizing Antibody Levels at Visit 5

Endpoint: *C difficile* toxin A–specific neutralizing antibody levels for each regimen expressed as adjusted GMCs, adjusted for baseline antibody level.

- Analysis time point: Visit 5 (Month 7)
- Analysis population: EI7 population (and mITT population as appropriate)
- Analysis methodology: GLM procedure to calculate adjusted GMC ratio (2-dose/3-dose) and the 95% CI
- Supporting objective: primary immunogenicity objective of noninferiority.

Reporting results:

• Two-sided 95% CI for the adjusted GMC ratio (2-dose/3-dose).

Endpoint: *C difficile* toxin B–specific neutralizing antibody levels for each regimen expressed as adjusted GMCs, adjusted for baseline antibody level.

- Analysis time point: Visit 5 (Month 7).
- Analysis population: EI7 population (and mITT population as appropriate).
- Analysis methodology: GLM procedure to calculate adjusted GMC ratio (2-dose/3-dose) and the 95% CI.
- Supporting objective: primary immunogenicity objective of noninferiority.

Reporting results:

• Two-sided 95% CI for the adjusted GMC ratio (2-dose/3-dose).

Endpoint: *C difficile* toxin A–specific neutralizing antibody levels for each regimen expressed as the percentage of participants achieving seroresponse.

- Analysis time point: Visit 5 (Month 7).
- Analysis population: EI7 population (and mITT population as appropriate).
- Analysis methodology: Miettinen and Nurminen procedure to calculate percentage difference in seroresponse (2-dose minus 3-dose) and the 95% CI.
 - Supporting objective: primary immunogenicity objective of noninferiority.

Reporting results:

• Two-sided 95% CI for the percentage difference in seroresponse (2-dose minus 3-dose).

Endpoint: C difficile toxin B—specific neutralizing antibody levels for each regimen expressed as the percentage of participants achieving seroresponse.

- Analysis time point: Visit 5 (Month 7).

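### Optional gain: the Month 7 seroresponse interval is valid but does not use the toxin-specific baseline serostatus that the SAP already derives

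*SAP*

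**What the plan says.** SAP Section 5.1.1 sets the decision rule for the seroresponse difference: "The difference in percentage of participants achieving seroresponse and the associated 95% CIs will be calculated using the Miettinen and Nurminen method". Section 6.1.1.1 repeats it for each toxin at Month 7 as a "Miettinen and Nurminen procedure to calculate percentage difference in seroresponse (2-dose minus 3-dose) and the 95% CI", and Section 6.2.1 does the same at Month 12. None of these places names a stratification factor or covariate.

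SAP Section 3.4.3 nevertheless defines a pre-dose classification for each toxin: "baseline serostatus (prior to the first vaccination) will be defined based on the LLOQ values". The GMC ratio, the other coprimary measure, does use baseline: Section 5.2.2 specifies an analysis of covariance "with baseline antibody levels as a covariate and dose regimen as a fixed factor".

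The handling of values below the LLOQ has also changed. In the Protocol Synopsis such values "will be set to 0.5 × LLOQ for analysis". In SAP Section 1 (Table 1) they "are imputed to the appropriate LLOQ value when determining seroresponse".

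**The concern.** The primary objective is met only if all four comparisons succeed (GMC ratio and seroresponse difference, for each toxin). In the SAP's own tables, toxin A seroresponse has the lowest power: 93.93%, against 96.99%, 99.7% and 99.92% for the others. It is therefore the comparison with most to gain from a tighter interval.

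Serostatus is measured before the first dose, and the baseline value is already needed to compute a 4-fold rise, so stratifying on it excludes nobody. If seroresponse rates differ between seronegative and seropositive participants, the unstratified interval carries between-stratum variance that a stratified interval removes. At stake is a modest amount of power. The validity of the planned test is not in question.

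**Working it through.** **Inputs.** From SAP Section 2.2.2: toxin A 82.3% (3-dose) and 79.3% (2-dose); toxin B 92.4% and 89.4%; 784 evaluable per arm; margin 10 points; two-sided 95% interval. The seropositive share w and the gap g in response rate between strata are not in the documents. They are assumed here: w from 30% to 70%, g from 0 to 30 points in either direction, and a regimen effect of -3 points in both strata.

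**Reproducing the plan's power.** Power = Φ((0.10 - 0.03)/SE - 1.96).
- Toxin A: SE = √[(0.823×0.177 + 0.793×0.207)/784] = √(0.309822/784) = 0.01988. Then 0.07/0.01988 - 1.96 = 1.56, so power is 94.08%. A restricted-variance (score) calculation gives 93.94%, against 93.93% stated.
- Toxin B: 99.79% by the simple formula and 99.70% by the score calculation, against 99.7% stated.
- Overall: 0.9691 × 0.9364 = 90.7%, as stated.

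**Validity of the planned interval.** At a true difference of -10 points, simulated one-sided type I error was 2.45% to 2.56%, with serostatus gaps up to 30 points.

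**What stratifying removes.** The variance sum falls by w(1 - w)g² in each arm. For toxin A with equal strata:

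| Gap | Variance sum | Reduction | Power, simple formula |
|---|---|---|---|
| 0 | 0.3098 | 0% | 94.1% |
| 10 points | 0.3048 | 1.6% | 94.4% |
| 20 points | 0.2898 | 6.5% | 95.4% |
| 30 points | 0.2648 | 14.5% | 96.8% |

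**Simulation of the stratified Miettinen-Nurminen interval** (Mantel-Haenszel weights, 200,000 runs per scenario, toxin A). The gains are slightly smaller than the simple formula gives. Ranges cover 30%, 50% and 70% seropositive and both directions of the gap, where feasible:
- no gap: 0.0 points
- 10-point gap: 0.2 to 0.3
- 20-point gap: 0.8 to 1.1
- 30-point gap: 2.1 to 2.3

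Toxin B gained 0.00 to 0.12 points, for gaps up to 20 points where feasible.

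**Type I error of the stratified interval** (400,000 runs per scenario): 2.45% to 2.56% with a common -10 effect. It was 2.11% to 2.73% when the overall effect was -10 but the effect in seropositives was -5 or -15. With only 1% to 5% seronegative and a fewer-than-5 fallback rule, it was 2.49% to 2.55%.

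**What the reference rates can and cannot show.** Protocol Table 7 lists 91.8% for toxin A under "Observed % of seroresponse from 3-dose group". SAP Table 4 gives 82.3%, with the note that "antibody concentration levels below the LLOQ or denoted as BLQ will be set to the appropriate LLOQ value". Changing the imputed value from 0.5 × LLOQ to LLOQ raises the bar from 2 × to 4 × LLOQ for seronegative participants and changes nothing for seropositive ones. If both figures come from the same samples and assay, the drop of 91.8 - 82.3 = 9.5 points falls wholly on seronegatives. With 30% seronegative, their 3-dose rate would be at most 1 - 0.095/0.30 = 68.3%. The seropositive rate would be at least (0.918 - 0.30)/0.70 = 88.3%, a gap of 20 points or more. From 53.7% seronegative, a zero gap is possible.

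**The case against.** The strongest objection is that nothing is broken. The interval holds its error rate, the stated powers reproduce, and a 10-point gap buys only 0.2 to 0.3 points of power for a change that might need a protocol amendment. This stands, and it is why the point is only one to consider. Nor is it an inconsistency that the GMC analysis adjusts for baseline: baseline already enters seroresponse through the 4-fold rise.

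A reader might infer from the fall from 91.8% to 82.3% that a minimum gain is guaranteed. The documents do not support that, for three reasons.
- Table 7's footnote names the reference study but not the assay, whereas Table 6's footnote names the new assay. Same samples and assay is therefore an assumption.
- Table 7's powers do not follow from its rates. By the formula above, 91.8% vs 86% gives about 76% (stated 96.14%), and 93.7% vs 86% gives about 33% (stated 97.18%).
- Both reference rates describe the 3-dose arm only. If the 2-dose arm has a smaller gap, the gain shrinks. At 30% seronegative it is about 1.0 point with an equal gap in both arms, but 0.4 to 0.6 with a 2-dose gap of zero or half that size. At 20% seronegative it falls from about 2.6 to between 0.8 and 1.6.

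A reader might also cite the remark in Protocol Section 2.2.3.2 about baseline-seronegative participants. It compares two 3-dose schedules, is most marked for toxin B and gives no rates. It does not support a toxin A gap between 2 and 3 doses.

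Finally, the benefit is concentrated in toxin A for power only. In proportional variance, the same 10-point gap with equal strata removes more for toxin B (0.005/0.164988 = 3.0%) than for toxin A (1.6%). Toxin B simply has almost no power left to gain.

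**Conclusion.** The point holds as an optional efficiency gain. The stated seroresponse interval is valid and visibly unstratified, and a suitable stratifier is already defined in the SAP. Other uses of serostatus may sit in redacted sections, but the decision rule is legible.

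For toxin A at Month 7 the gain in power runs from 0 to about 2 points for serostatus gaps from 0 to 30 points. This assumes the SAP's planning rates, 784 per arm and a -3 point effect in both strata. These are illustrations, neither minimum nor maximum gains. With no gap, stratifying cost no power in simulation. Month 12 cannot be sized, because the documents give no Month 12 rates.

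**What to change.** Before the Month 7 snapshot, when Protocol Section 6.3.3 has the sponsor team unblinded, amend SAP Sections 5.1.1 and 6.1.1.1 (and 6.2.1 for consistency) as follows:
- The interval for each toxin is a Miettinen-Nurminen interval stratified by that toxin's baseline serostatus, with Mantel-Haenszel weights.
- If either stratum has fewer than 5 participants in either arm, the unstratified interval is used.
- The unstratified interval is otherwise reported as supportive.

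If unblinding has already occurred, leave the primary analysis as it is and report the stratified interval as supportive only.

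The change needs no new data and no change of margin or estimand. It costs SAP wording and minor programming. A protocol amendment is also needed if the change counts as a major modification of the primary analysis under Protocol Section 9 and SAP Section 2. The statistical price is the small shift in type I error shown above if the regimen effect differs by serostatus.
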